2.1.2 Effectiveness Results

Procedural success, defined as the successful creation of an endoAVF with blood flow confirmed intraoperatively by fistulography or postoperative duplex ultrasonography, was achieved in 96.7% (88/91) of the population. Using Kaplan-Meier (KM) point estimates at month 6, the cannulation success rate was $84.9\% \pm 5.3\%$ for participants in the HD subset. The mean time to cannulation was 2.0 ± 1.6 months.

Primary patency and cumulative patency were determined using the KM point estimates at month 6. Primary patency was $72.4\% \pm 5.2\%$ and cumulative patency was $77.3\% \pm 5.0\%$. Functional patency was 100% through 6 months in the population who used their endoAVF for HD.

2.2 Clinical Investigation General Rationale

The purpose of this clinical investigation is to provide clinical evidence to further demonstrate reasonable assurance of safety and effectiveness of the WavelinQTM EndoAVF System for endovascular fistula (endoAVF) creations in a post-market confirmatory interventional fashion. See Section 3 for specific objectives and Section 4.5 for endpoint rationales.

2.3 Investigation Device Description

The WavelinQTM EndoAVF System, manufactured by the Sponsor, is indicated for the cutting and coagulation of blood vessel tissue in the peripheral vasculature for the creation of an AVF used for HD. The device is intended to be used in patients suffering from chronic kidney disease requiring HD by physicians trained and experienced in endovascular techniques (Refer to Section 12.2 for training requirements). The WavelinQTM EndoAVF System will be used for these intended purposes as part of this clinical investigation according to its IFU.

The WavelinQTM EndoAVF System consists of two 4 Fr, single-use, disposable, magnetic, hydrophilic coated catheters: (1) a venous catheter powered by an Electrosurgical Unit (ESU) and (2) an arterial catheter. The system has been developed for use with commercially available accessories including the ESU, an electrosurgical pencil, grounding pads, an arm board, fixation straps, and a remote hand switch.

The venous catheter is a flexible magnetic catheter that contains a radiofrequency (RF) electrode, a hemostasis valve crosser for interfacing with the introducer sheath on the distal end and features a cable and plug for the delivery of RF energy on the proximal end. RF energy is delivered by connecting the venous catheter to the ESU via the electrosurgical pencil and is used with standard grounding pads.

The arterial catheter is a flexible magnetic catheter which contains the backstop for receiving the electrode from the venous catheter.

When placed in proximity, the magnets contained in each catheter attract each other, while aligning the electrode with the backstop. Rotational indicators are present in each catheter for use to accurately position the catheters. Once correctly aligned, RF energy can then be delivered through the electrode for cutting and / or coagulating tissue to create the endoAVF. The full procedural steps and associated information are detailed in the device IFU.

NOTE: If the participant has more than one brachial vein, embolization of one of the brachial veins is recommended to divert flow to the superficial veins to facilitate maturation of the endoAVF.

3 CLINICAL INVESTIGATION DESIGN

This is a global, multi-center, prospective, post-market, confirmatory, interventional, non-randomized, single-arm, clinical investigation to further demonstrate the safety and effectiveness of the WavelinQTM EndoAVF System for endovascular fistula creations in the ulnar and radial vessels when accessed from the wrist (and / or upper arm) arteries and concomitant veins in the parallel or anti-parallel configuration.

Safety objective: The safety outcome of participants receiving treatment with the WavelinQTM EndoAVF System will be compared to a Performance Goal (PG) derived from the prior clinical investigations evaluating the WavelinQTM EndoAVF System to confirm that the safety profile of the device is maintained.

Effectiveness objectives: The effectiveness measure evaluated through the primary effectiveness endpoint will be used to assess the performance of the WavelinQTM EndoAVF System when used in the creation of AVFs in a post-market fashion. The clinical investigation will aim to evaluate the number of interventions per patient year (PY) to facilitate (facilitation interventions) and maintain (maintenance interventions) use of the AVF and compare this to clinical guideline recommendations. Non-hypothesis tested secondary endpoints will evaluate the performance of the endovascularly created AVFs with respects to short-term (maturation / cannulation) and long-term (functional cumulative patency) performance characteristics.

A total of approximately one-hundred and fifty (150) treated participants will be included. Note that as per the definition of treated participant (refer to Section 6.2), this number does not include the participants into whom the WavelinQTM EndoAVF System was introduced but in whom procedure success (as defined in Section 4.3) was not achieved (estimated to total approximately ten [10] participants).

Under the current enrollment assumptions, a target of approximately 15 investigational sites (up to a maximum of 30 investigational sites) may participate globally. This investigation will enroll participants who are either already receiving HD at the time of screening (prevalent participants), regardless of access type (CVC, AVF, and / or AVG), or those who are not yet receiving HD but are in need of a vascular access as determined by the referring clinician (incident participants).

Treated participants will be followed for 24-months post index procedure. The enrollment period is estimated to last about 18 months and the total clinical investigation duration is estimated to last 3.5 years from the enrollment of the first participant to the last follow-up visit of the last active treated participant. The primary endpoints will be analyzed when the last active treated participant has completed their 6-month follow-up. A final analysis will be completed when all participants have completed, or prematurely discontinued before, their 24-month follow-up.

4 CLINICAL INVESTIGATION ENDPOINTS

4.1 Primary Endpoints

There are two co-primary endpoints for this clinical investigation: An endpoint to evaluate safety and another to evaluate effectiveness. These endpoints are defined in this section.

4.1.1 Primary Safety Endpoint

Safety through 30 Days

The primary safety endpoint is the proportion of participants with freedom from Clinical Events Committee (CEC) adjudicated device- or procedure-related serious adverse events (SAEs) through 30 days.

The primary safety endpoint will be evaluated against a PG of 82.6%, which was set with a 10% non-inferiority margin of the estimated 92.6% through 30 days derived from premarket data from the prior clinical investigations evaluating the WavelinQTM EndoAVF System.

4.1.2 Primary Effectiveness Endpoint

Interventions Post Creation to Facilitate AVF Use and / or Maintain AVF Use (Facilitation and / or Maintenance Interventions) through the Timepoint of the 6-Month Follow-Up of the Last Active Treated Participant

The primary effectiveness endpoint is the number of interventions post creation to facilitate and / or maintain AVF use (facilitation interventions and / or maintenance interventions as defined in Section 4.4). The procedures that will be evaluated as part of this endpoint are indicated in Table 1 in Section 4.4 and exclude adjunctive and second stage procedures.

The number of facilitation and / or maintenance interventions per PY will be compared to a PG that is composed of the combined targets for interventions to facilitate and maintain AVF use recommended by the 2019 update of the KDOQI Clinical Practice Guideline for Vascular Access.⁸ This endpoint will be evaluated including all data collected for all participants up until the timepoint of the 6-month follow-up of the last active treated participant (i.e. including any and all data exceeding the 6-month follow-up visit up to this timepoint).

4.2 Secondary Endpoints

The secondary endpoints will be evaluated in a descriptive fashion and will be analyzed through the timepoints specified for each endpoint below. These endpoints will be reported at the timepoints specified in Section 7.9.

4.2.1 Safety

• Device and Procedure Related SAEs

The proportion of participants with freedom from CEC adjudicated device-related or procedure-related SAEs (refer to Section 8 for definitions). This endpoint will be assessed through 6- and 24-months post creation.

4.2.2 Effectiveness

• Physiological Maturation

The proportion of participants with AVFs that meet the definition of physiological maturation. Physiological maturation is defined as an AVF having at least 500 mL/min of flow in the brachial artery and an outflow vein diameter of ≥ 4 mm as measured by DUS. ^{16,17} Participants with AVFs that meet the definition of functional maturation (Refer to Section 4.3) will automatically meet physiological maturation. This endpoint will be assessed through 6-weeks post creation.

• Cannulation Success

The interval of time between HD arteriovenous (AV) access creation to first successful use for HD using 2-needle cannulation and proportion of participants with successful first use for HD using 2-needle cannulation. This endpoint will be assessed through 6-months post creation.

• Cumulative Functional Patency

The time from first successful HD AV access use for HD using 2-needle cannulation to access abandonment, when the access reaches an access censoring event as specified a priori in this CIP, or analysis timepoint / clinical investigation end. This endpoint will be assessed through 12-months post creation.

4.3 Exploratory Endpoints

The following endpoints may be evaluated in an exploratory fashion. Data will be collected throughout the course of the investigation in support of these endpoints.

• Procedure Success

The proportion of participants with successful endoAVF creation using the WavelinQTM EndoAVF System as confirmed via intraprocedural angiography and / or verified via DUS.

• Adjunctive Procedures

The number of adjunctive procedures performed (see Section 4.4 for definition).

• Vascular Access at HD Initiation

The vascular access HD modality used at the initiation of HD following the index procedure (CVC, AVG, clinical investigation AVF, or alternate AVF). Use of the clinical investigation AVF at initiation includes both one- and two-needle cannulation and may be presented as a combined total as well as by type of needle access. This endpoint applies to the incident participant population only.

• Physiological Maturation

As defined for the secondary endpoint (see Section 4.2.2) evaluated through additional time intervals.

• Cannulation Success

As defined for the secondary endpoint (see Section 4.2.2) evaluated through additional time intervals.

Functional Maturation

The proportion of participants with successful prescribed HD with 2-needle cannulation of the AVF for three (3) continuous weeks. Additionally, the time from HD AV access creation to the first day of the 3-week period.

• Functional HD Usability

The proportion of participants dialyzed using successful 2-needle access of the AVF created as part of this clinical investigation for $\geq 75\%$ of HD sessions over a continuous 28-day period. Additionally, the time from HD AV access creation to the first day of the 28-day period.

• Interventions

Intervention related endpoints are categorized as follows:

- Interventions Post Creation to Facilitate AVF Use (Facilitation Interventions)
 As defined for the primary effectiveness endpoint (see Section 4.1.2) evaluated separately.
- Interventions Post Creation to Maintain AVF Use (Maintenance Interventions)
 As defined for the primary effectiveness endpoint (see Section 4.1.2) evaluated separately.
- All Interventions Post Creation (Facilitation, Maintenance and HD Continuity Interventions)

For this endpoint, the number of interventions post creation will include all interventions (facilitation, maintenance, and HD continuity interventions) in Table 1 of Section 4.4 but exclude adjunctive and second stage procedures.

• All Interventions After First Use (Facilitation, Maintenance and HD Continuity Interventions)

As defined for the exploratory endpoint directly above with duration of evaluation adjusted to start from first successful HD AV access use.

• Primary Patency

The time from HD AV access creation to the first one of the following events: access thrombosis; any facilitation or maintenance intervention intended to support maturation or cannulation, as well as those to maintain, or re-establish functionality*; access abandonment (as defined in Section 4.4); the access reaches an access censoring event as specified a priori in this CIP; or analysis timepoint / clinical investigation end. *Excludes adjunctive and second stage procedures.

• Cumulative Patency

The time from HD AV access creation to access abandonment, when the access reaches an access censoring event as specified a priori in this CIP, or analysis timepoint / clinical investigation end.¹⁸

• Primary Functional Patency

The time from first successful HD AV access use for HD using 2-needle cannulation to the first one of the following events: access thrombosis; any facilitation or maintenance intervention intended to support maturation or cannulation as well as those to maintain or re-establish functionality*; access abandonment (as defined in Section 4.4); the access reaches an access censoring event as specified a priori in this CIP; or analysis timepoint / clinical investigation end. *Excludes second stage procedures.

• Cumulative Functional Patency

As defined for the secondary endpoint (see Section 4.2.2.2) evaluated through additional time intervals.

• CVC Exposure / Use

Data will be collected regarding CVC exposure and use.

- For participants with a CVC in place at the index procedure, data will be collected after HD AV access creation to investigate the duration of CVC use.
- For all participants, data will be collected to determine frequency of CVC placements, time to CVC removal, total days of CVC exposure, and total days of CVC use.

• DUS Juxta/Peri-Anastomotic Area and Perforator Vein Patency

Data will be gathered using DUS examinations to evaluate the presence and characteristics of thrombosis and stenosis within the juxta-anastomotic area (defined as the arterial area extending 5cm before and the venous area extending 5cm after the anastomosis) and peri-anastomotic area (defined as the venous area extending from the juxta-anastomosis area to the start of the perforating vein) as well as within the perforator vein for all participants through 6 weeks.

• Wrist Arterial Procedure Access Considerations

Data will be gathered using DUS examinations to evaluate the presence and characteristics of thrombosis and stenosis in arteries at the wrist used for procedure access during the index procedure. Images from these DUS examinations will be submitted to the Core Lab for review and assessment. Additionally, data will be captured for these participants on procedure-related AEs that are attributable to arterial access at the wrist as adjudicated by the CEC.

• Participant Satisfaction and Quality of Life (QOL):

The Short Form-Vascular Access Questionnaire (SF-VAQ) and the European Quality of Life-5 Dimensions (EQ-5D) will be used to gather data on the participants QOL at the time points specified in Section 1.3 and Section 6.

• HD AV Access Continuity

HD AV access continuity is defined as the ability for a participant to receive an alternate HD AV access in the same arm as the index AVF. This endpoint applies to participants for whom their index AVF is abandoned. The alternate type(s) of HD AV access(es) placed in these participants will be collected.

4.4 Applicable Endpoint Definitions

Access Abandonment (permanent abandonment) is defined as the point at which the access can no longer be used for one or two needle prescribed HD as it may be unable to provide adequate flows and / or is deemed unsafe for the participant, and the associated problem cannot be corrected by any further intervention, including medical, surgical, or endovascular interventions or rest.^{8,19} Participants with an abandoned index AVF will continue with follow-up through 24-months and data will be collected on safety and interventions.

A HD AV access is not considered abandoned:

- If the participant discontinues use of the AV access due to kidney transplant, initiation of PD, or participant preference.
- During the maturation period or while waiting for a second stage procedure unless the principal investigator (PI) determines the participant requires and they then receive an alternative HD vascular access.

- During planned interventions, including transposition.
- If all reasonable efforts have not been attempted (and documented) to improve the condition of the access for it to be used.

A discontinuation of use of the clinical investigation AVF for any reason that does not meet this definition of access abandonment will be considered a temporary interruption.

Access Circuit Censoring Events include participant transfer to PD, kidney transplantation or the event of a participants premature discontinuation in the investigation due to withdrawn consent, withdrawal by PI, Lost to Follow-Up (LTF), or participant death (refer to Section 6.5 for definitions).

Adjunctive Procedure(s): Procedure(s) completed during the index procedure (prior to leaving the procedure room) as part of Standard-of-Care (SOC) procedures. These may include procedures to facilitate maturation and / or cannulation of the AVF, procedures to maintain use of the AVF, procedures to ensure HD continuity, as well as procedures to address AFs.

Second Stage Procedure(s): Facilitation Interventions (as defined below) intended to support the cannulation of arterialized vein segments that are determined to be needed a priori to or at the time of the index procedure (i.e. pre-planned facilitation interventions intended to support cannulation). Second stage procedures will not count against the intervention or patency endpoints and will require completion of the Second Stage Procedures eCRF.

Intervention(s): Clinical investigation participants may require procedures that are not predetermined or planned that are performed *after* the index procedure (adjunctive procedures are those performed *during* the index procedure and second stage procedures are expected procedures that are determined a priori or at the time of the index procedure). Interventions require the completion of the Intervention eCRF. For this clinical investigation, interventions are further classified as follows and delineated by endpoint in Table 1:

- Facilitation Intervention(s): Defined as those procedures that are intended to facilitate functionality of the index AVF (i.e. those intended to support the maturation or cannulation of arterialized vein segments) and / or a procedure to address an AE related to the facilitation of index AVF functionality.
- *Maintenance Intervention(s)*: Defined as those procedures that are intended to maintain / re-establish functionality of the index AVF and / or a procedure to address an AE related to the maintenance of index AVF functionality.
- *HD Continuity Intervention(s)*: Defined as those procedures that are intended to ensure the continuity of HD (not including diagnostic studies) other than those related to the facilitation or maintenance of index AVF functionality and / or a

procedure to address an access related AE other than those related to the facilitation or maintenance of index AVF functionality. HD continuity interventions include all CVC related interventions up until the placement of a subsequent AV access following abandonment of the index AVF. HD continuity interventions exclude any intervention performed on a non-index AV access other than the placement of the non-index AV access itself.

Table 1: Eligible Interventions and Classification by Intervention Endpoint

	Facilitation I	Interventions	35	HD Continuity Interventions	
	Support of AVF Maturation	Support of AVF Cannulation	Maintenance Interventions		
Applicable to Endpoint:	• Angioplasty / Balloon-Assisted- Maturation • Embolization of collaterals (coiling, plugging, or ligation) • Stent / stent graft • Surgical revision	Superficialization / elevation Transposition	• Angioplasty** • Banding • Embolization of collaterals (coiling, plugging, or ligation)# • Stent / stent graft • Surgical revision • Thrombectomy / thrombolysis • Treatment of aneurysm / pseudoaneurysm • Treatment of AV access infection	•Access ligation •AVF placement •AVG placement •CVC placement •Fibrin sheath removal •Treatment of infection	
Primary Effectiveness: Maintenance and / or Facilitation	Yes	Yes*	Yes	No	
Exploratory: Facilitation	Yes	Yes*	No	No	
Exploratory: Maintenance	No	No	Yes	No	
Exploratory: All Interventions	Yes	Yes*	Yes	Yes	

Excludes second stage procedures.

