Intervention(s)	Procedures that are not pre-determined or planned that are performed after the index procedure (adjunctive procedures are those performed during the index procedure and second stage procedures are expected procedures that are determined a priori or at the time of the index procedure). Interventions require the completion of the Intervention eCRF. For this clinical investigation, interventions are further classified as facilitation, maintenance, and HD continuity interventions (Refer to Table 1).
Investigational Site	Institution or site where the clinical investigation is carried out.
Juxta-Anastomotic Area	Defined as the arterial area extending 5cm before and the venous area extending 5cm after the anastomosis.
Legally Authorized Representative (LAR)	Individual or judicial or other body authorized under applicable law to consent, on behalf of a prospective participant, to the participant's participation in the clinical investigation. "Legally designated representative" or "legally acceptable representative" are other terminologies used under national regulations for "legally designated representative".

Term	Definition
Lost to Follow-Up (LTF)	A participant may be considered LTF if the investigation site team members are unable to locate the participant despite three documented attempts to notify the participant via telephone and, if necessary, a certified letter to the participant's last known mailing address or local equivalent methods. This does not apply to missed visits, where the participant misses one of the follow up contact time points but completed a subsequent one (when participant misses two consecutive follow-ups and is unable to be contacted with the documented attempts outlined before, the participant may be considered LTF and withdrawn from the clinical investigation). The site should also contact the HD center to ascertain the participant's status. Before the site considers a participant LTF, written agreement should be obtained from the Sponsor.
Maintenance Interventions	Defined as those procedures that are intended to maintain / re-establish functionality of the index AVF and / or a procedure to address an AE related to the maintenance of index AVF functionality.
Malfunction	Defined as a failure of a medical device to perform in accordance with its intended purpose when used in accordance with the IFU or CIP.

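### The CIP classifies planned maturation-support procedures done after the index procedure inconsistently, so they can be left out of the co-primary intervention rate.

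*Protocol*

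**What the plan says.** Four parts of the CIP decide whether a procedure enters the numerator of the primary effectiveness rate.

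- **Intervention (CIP 4.4, Appendix B).** CIP 4.4 reads "Clinical investigation participants may require procedures that are not predetermined or planned that are performed" after the index procedure. Appendix B has the same limit: "Procedures that are not pre-determined or planned that are performed" after the index procedure. These procedures go on the Intervention eCRF.
- **Second stage procedure (CIP 4.4, Appendix B).** The formal definition is limited to "pre-planned facilitation interventions intended to support cannulation". These go on their own eCRF and do not count against the intervention or patency endpoints. The parenthesis inside the Intervention definition is wider: "second stage procedures are expected procedures that are determined a priori or at the time of the index procedure", with no mention of cannulation.
- **Facilitation intervention (CIP 4.4).** This covers "those intended to support the maturation or cannulation of arterialized vein segments" and carries no planned or unplanned test of its own.
- **Endpoint (CIP 4.1.2, Table 1).** The counted procedures "exclude adjunctive and second stage procedures". In the Table 1 row "Primary Effectiveness: Maintenance and / or Facilitation", the asterisk for the second stage exclusion is on the cannulation column. The maturation column is an unqualified yes.

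Adjunctive procedures are confined to the index procedure itself. SAP 5.1.2 counts dated entries on the Post-Procedure Intervention page that are typed as facilitation and/or maintenance. SAP 5.3.7 takes the intervention failures for primary patency from the same page.

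**The concern.** Take a balloon-assisted maturation or a collateral embolization that is scheduled at the index procedure and done some weeks later. It is too late to be adjunctive. It supports maturation, so it falls outside the formal second stage class. It is planned, so the Intervention definition does not admit it. Under the wider parenthesis it could pass as second stage and be excluded. Under CIP 4.1.2 and Table 1, nothing excludes it.

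The classification decides which form a site completes, and the form decides whether the SAP counts the event. The study is single-arm and unblinded, is compared with a fixed goal of 5/PY, and may run at up to 30 sites. Sites could reasonably read the text differently. An omission can only lower the co-primary rate and remove a failure from exploratory primary patency. The rate is also reported with a confidence interval as a measure of burden (CIP 4.5.1), so understating it matters even when the test passes.

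**Working it through.** **1. The same procedure under each passage** (maturation support, planned by the time of the index procedure, done later)

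| Passage | Result |
|---|---|
| CIP 4.4 and Appendix B, Intervention | Not an intervention, because planned |
| CIP 4.4 and Appendix B, formal second stage | Not second stage, because not cannulation support |
| CIP 4.4, parenthesis on second stage | Second stage, hence excluded |
| CIP 4.4, adjunctive | Not adjunctive, because done later |
| CIP 4.1.2 and Table 1 | Not excluded |
| SAP 5.1.2 | Counted only if entered on the Post-Procedure Intervention page |

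CIP 4.4 is also loose with the term itself. It calls second stage procedures facilitation interventions, and its abandonment rules speak of planned interventions, although the parent definition says interventions are unplanned.

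**2. The plan's own figure.** Inputs from CIP 7.3: 3.0/PY assumed, goal 5/PY, more than 100 PY, two-sided alpha 0.05. At 100 PY the null mean is 5 × 100 = 500 events. Both the exact lower 2.5% Poisson tail and the Wald interval on the log rate (count × exp(1.96/√count) < 500) give success at 456 events or fewer, which is 4.56/PY. The attained one-sided error is 0.0246. Power at 3.0/PY exceeds 99.99%, so the stated figure of over 99% is confirmed.

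**3. Exposure.** Assumptions: uniform accrual over the stated 18 months, and linear attrition between the stated 20%, 40% and 60% losses at 6, 12 and 24 months. Follow-up at the cutoff then runs from 6 to 24 months. Mean accumulated follow-up is 7.6 months for those with 6 to 12 months of potential follow-up and 12.8 months for those with 12 to 24. Weighted: (6 × 7.6 + 12 × 12.8)/18 = 11.07 months. Then 150 × 11.07/12 ≈ 138 PY. The SAP also ends exposure at permanent abandonment, so I use 100 to 138 PY as the range.

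**4. Effect on the rate.** If a share f of the 150 treated participants each has one uncounted procedure, the rate falls by 150 × f / PY. The share is an assumption.

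| f | Events omitted | Fall at 138 PY | Fall at 100 PY |
|---|---|---|---|
| 10% | 15 | 0.11 | 0.15 |
| 30% | 45 | 0.33 | 0.45 |
| 50% | 75 | 0.54 | 0.75 |

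**5. Effect on the decision at 100 PY.** Suppose the true rate, with all such procedures included, is 5.0/PY. The counted mean is 500 − 150f, and success is 456 events or fewer.

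| f | Counted mean | Chance of success |
|---|---|---|
| 0 | 500 | 0.025 |
| 5% | 492.5 | 0.051 |
| 10% | 485 | 0.097 |
| 20% | 470 | 0.268 |
| 30% | 455 | 0.531 |

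Now suppose the counted rate is the planned 3.0/PY and the procedures come on top. With one in 50% of participants the full mean is 300 + 75 = 375, and the chance of success if all were counted is still above 99.9%. To move the full rate from 3.0/PY to the pass boundary would take (4.56 − 3.0) × 100/150 ≈ 1.0 uncounted procedure per treated participant at 100 PY, or (4.6 − 3.0) × 138/150 ≈ 1.5 at 138 PY (boundary about 4.6/PY).

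**The case against.** The strongest reply is that the SAP, not the CIP definition, produces the number. SAP 5.1.2 has no planned or unplanned test, and the CIP follow-up sections ask sites for any access circuit interventions. The Second Stage form is formally for cannulation support, so the Intervention page is the natural home for a staged maturation procedure. This stands in part: a site may well enter the procedure, and then it counts. A reader might infer that these procedures necessarily vanish from the endpoint, but the documents support only that they can. The SAP cannot recover an event that a site, following the CIP definition, did not put on that page. SAP 6.15 would describe one filed as second stage, but it would not be in the rate.

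Second, Table 1 lists eligible procedure types and does not say that planned maturation procedures count. That is correct. The point is only that neither Table 1 nor CIP 4.1.2 excludes them.

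Third, on the wider parenthesis the classes leave no gap. But the procedure is then excluded outright, against the formal definition and Table 1, so the inconsistency remains.

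Fourth, no passage describes a planned later maturation procedure. The one maturation step recommended in advance, brachial vein embolization, appears under adjunctive procedures in CIP 6.2.2. This stands as a limit on frequency. The CIP does not say how that step is classed if done later. The eCRF pages and the content of the SAP's derived data specification are not in the text available, and form instructions there could settle the matter.

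**Conclusion.** The inconsistency is real and bears on the numerator of a co-primary endpoint. A planned, post-index maturation-support procedure can be left out of the rate and out of exploratory primary patency failures, depending on the form used, and every omission favours the device.

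The size is about 0.11 to 0.15/PY for each assumed 10% of treated participants with one uncounted procedure. The share is not in the documents, and the range rests on 100 to 138 PY.

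A reader might conclude that the trial's power or its pass/fail result is in doubt. The figures do not support that at the planned 3.0/PY, where the boundary is about 1.6/PY away. The decision is sensitive only when the true rate is near the goal: at 5.0/PY and 100 PY, a 10% share takes false success from 0.025 to about 0.10. No sample-size figure is wrong. The change is worth making because it is cheap and the reported rate is itself a result.

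**What to change.** Reconcile the passages before database lock.

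1. In CIP 4.4 and Appendix B, define Intervention(s) as any facilitation, maintenance or HD continuity procedure performed after the index procedure, planned or not, except second stage procedures as formally defined (pre-planned cannulation support). HD continuity must stay in the parent definition because the exploratory all-interventions endpoints depend on it.
2. Align the parenthesis on second stage procedures with the formal definition.
3. Require planned maturation-support procedures to be recorded on the Intervention eCRF, so that SAP 5.1.2 and 5.3.7 pick them up.

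Excluding planned maturation procedures could also be a legitimate choice. In that case CIP 4.1.2 and Table 1 must say so, and the SAP should add a sensitivity analysis that counts all post-index facilitation and maintenance procedures, planned or not. For this, those procedures still have to be recorded.

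The cost is a CIP wording change and a form-completion instruction, with a check of planned procedures at sites already enrolling. The reported rate may be slightly less favourable. The change concerns counting only and alters no treatment.
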